9.2.2. Statistical Analysis of Pharmacokinetic Parameters

Plasma concentration-time data will be listed by dose, age group, and summarized using descriptive statistics (median, minimum, maximum, arithmetic mean, 95% confidence interval for the arithmetic mean, standard deviation, coefficient of variation ($CV = \sqrt{(exp(SD2) - 1) * 100 [NOTE: SD = SD of log transformed data]}$), geometric mean, 95% confidence interval for the geometric mean and standard deviation of logarithmically transformed data) by planned relative assessment time. Mean and/ or median values will be plotted over time. For tmax the following summary statistics will be calculated for each dose level, median, maximum, minimum, arithmetic mean, 95% confidence interval, and standard deviation will be calculated.

Individual plasma pharmacokinetic parameters values as well as a descriptive summary (median, minimum, maximum, arithmetic mean, 95% confidence interval for the arithmetic mean, standard deviation, coefficient of variation ($CV = \sqrt{\exp(SD2)} - 1$) * 100 [NOTE: SD = SD of log transformed data]), geometric mean, 95% confidence interval for the geometric mean and standard deviation of logarithmically transformed data) by dose cohort and age group will be reported. All PK parameters will be reported to at least 3 significant digits, but to no more significant digits than the precision of the original data.

All PK parameters and concentration summaries will be reported to at least 3 significant digits, but to no more significant digits than the precision of the original data.

The following pharmacokinetic statistical analyses will only be performed, if sufficient data is available (i.e. if subjects have well defined plasma profiles).

9.2.2.1. Dose-Proportionality Analysis for Part 1 Dose Escalation Subjects

Dose proportionality analysis will be done for QD doses and BID doses separately. A minimum of 3 values per dose must be available for a given parameter to estimate dose proportionality with the power model.

Dose proportionality of log-transformed parameters $AUC(0-\infty)$ (or if not available AUC(0-t)) and Cmax will be assessed using the power model for, as described below:

 $y = \alpha * dose^{\beta}$

where y denotes the PK parameter being analysed and α depends on subject and error.

Dose proportionality implies that $\beta=1$ and will be assessed by estimating β along with its confidence interval. The exponent, β , in the power model will be estimated by regressing the log_e-transformed parameter on log_e-transformed dose:

 $\ln(y) = \ln(\alpha) + \beta * \ln(\text{dose})$

The power model will be fitted by restricted maximum likelihood (REML), for every dose level (treatment) with minimum 3 values. Both the intercept and slope will be fitted as random effects. The following SAS code will be used:

```
proc mixed data = DSETIN;
      class subject;
      model LNVAR=LNdose / solution alpha=0.1 outp=pred ddfm=kr;
      random intercept / type=UN subject=subject;
      ods output solutionf=solutionf;
run;
```

Point estimates for the slopes of PK parameters with associated CIs will be presented.

If this model fails to converge, the model will be refitted with slope as a fixed effect.

If the log transformed models are not proportional and sufficient data are available, log_etransformed dose-normalised AUC($0-\infty$) (or if not available AUC(0-t)) and Cmax will be analysed using a suitable mixed effects model, fitting treatment as a fixed effect and subject as a random effect. Point estimates and corresponding 90% confidence intervals for the ratios of each dose level to the reference dose level 1 will be determined using code similar to that outlined above.

```
proc mixed data = DSETIN;
     class subject treatment;
     model LN(VAR/dose) = dose / ddfm=KR outp=pred cmax;
     id dose usubjid;
     random usubjid;
     lsmeans dose;
     estimate "DL2 vs DL1" treatment 1 0 0 0 0 0 0 -1 /cl alpha=0.1 e;
     estimate "DL3 vs DL1" treatment 0 1 0 0 0 0 0 -1 /cl alpha=0.1 e;
     estimate "DL4 vs DL1" treatment 0 0 1 0 0 0 0 -1 /cl alpha=0.1 e;
     estimate "DL5 vs DL1" treatment 0 0 0 1 0 0 0 -1 /cl alpha=0.1 e;
     estimate "DL6 vs DL1" treatment 0 0 0 0 1 0 0 -1 /cl alpha=0.1 e;
     estimate "DL7 vs DL1" treatment 0 0 0 0 0 1 0 -1 /cl alpha=0.1 e;
     estimate "DL8 vs DL1" treatment 0 0 0 0 0 0 1 -1 /cl alpha=0.1 e;
     lsmeans treatment;
     ods output estimates=estimates lsmeans=lsmeans;
```

run:

The back-transformed estimate and 90% CI will be presented.

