4.2.2. Initial Dose Exploration (accelerated titration)

In order to minimize the number of subjects enrolled at sub-optimal doses, an accelerated titration design will be implemented until the first evidence of a non diseaserelated \geq Grade 2 toxicity, with the exception of toxicities listed in Section 4.2.4.2. One subject at each dose level will be enrolled, starting at the dose described in Section 4.7. If the subject enrolled at the first dose level experiences a dose-limiting toxicity (DLT), then lower doses (i.e., Dose Level -1) will be explored and re-escalation may be attempted based on safety and tolerability data. Accelerated titration will continue until a subject experiences a non-disease-related \geq Grade 2 toxicity, then the implementation of the MTD confirmation stage (Section 4.2.3) will be triggered. Each subject must complete the 21-day DLT evaluation period, and the available safety data must be reviewed before a decision is made on whether to proceed to the next dose level. If a subject fails to receive more than 80% of the planned doses within the 21-day DLT evaluation period for reasons other than toxicity, the subject will be replaced. Guidelines for selecting the next dose level are described in Section 4.2.4.2. Additional subjects may be enrolled at previously cleared dose levels if safety and PK analysis suggest this is warranted for better understanding the safety and PK profile. Safety assessments from these subjects will be included in the MTD determination.

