11.10.2.2.2. Statistical analysis of pharmacokinetic parameters

Plasma concentration-time data will be listed by dose, age group, and summarized using descriptive statistics (n, mean, SD, median, minimum and maximum) by planned relative assessment time. Mean and/ or median values will be plotted over time. Individual plasma and urinary (if available) pharmacokinetic parameter values as well as a descriptive summary (mean, standard deviation, median, minimum, maximum, geometric mean, and the standard deviation, coefficient of variance percent (CV%) and 95% confidence interval of log-transformed parameters [if applicable]) by dose cohort will be reported.

Cmax and AUC (AUC($0-\infty$), single dose, and AUC($0-\tau$), steady state) will be plotted as a function of the dose administered. If more than 2 dose cohorts are required to reach MTD (or the recommended dose based on available safety, PK and response data), dose proportionality of AUC and Cmax for GSK3326595 following single dose administration and AUC($0-\tau$) and Cmax following repeat dose administration will be assessed graphically and using the power model as described below:

 $\log (\text{pharmacokinetic parameter}) = a + b * \log(\text{dose})$

where a is the intercept and b is the slope.

The power model will be fitted by restricted maximum likelihood (REML) using Statistical analysis system (SAS) Proc Mixed. Both the intercept and slope will be fitted as fixed effects. If there is sufficient data, the model may also be fit with the intercept and/or slope as random effects depending on the ability of the model to converge and on estimation of variance-covariance matrix. The mean slope and corresponding 90% confidence interval will be estimated from the power model.

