2. SUMMARY OF KEY PROTOCOL INFORMATION

2.1. Changes to the Protocol-Defined Statistical Analysis Plan

There were no changes or deviations to the originally planned statistical analysis specified in the protocol amendment 8 (dated: 20/APR/2022).

Section 2.2 replicates what is in protocol amendment 8 (dated 20 April 2022).

In general, the plan will be to report all the primary and secondary outcomes, and none of the exploratory outcomes (including pharmacodynamics and genetics outcomes). The following is the exception to this plan:

- Additional secondary analyses, for Part 1 are investigator-assessed percent change from baseline, and maximum percent reduction from baseline in sum of diameters, and progression-free survival (PFS), defined as time from first dose until radiographic progression per standard criteria, or death due to any cause, whichever is earlier.
- All Part 2 ACC cohorts will be included in the overall survival analysis.
- Time to response listings will be included with duration of response analyses for ACC TN cohort.
- All NHL P53 cohorts are being compared as part of secondary analyses, not exploratory analyses.
- PK analyses are considered secondary.
- Progression free survival (PFS) rate at six months after starting GSK3326595 will be conducted as a secondary analysis for all Part 2 cohorts not including GBM (for which this is the primary analysis).
- Progression free survival (PFS) rate at six months after starting GSK3326595 will be estimated using Kaplan-Meier plots (only) as a secondary analysis for Part 1 and Part 3 cohorts.

White blood cells will be included with laboratory assessments summarized. (Section 8.4.2)

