15.12.9. Pharmacokinetic Tables

		IDSL / Example			
No.	Population	Shell	Title	Programming Notes	Deliverable
4.1	РК	PK01	Summary of GSK3326595 Pharmacokinetic Concentration- Time Data by Treatment and Study Day	Use descriptive statistics (n, mean, SD, median, min and max) by planned relative assessment time; concentrations in ng/mL. All planned time points. by dose for Part 1, by cohort for parts 2 and 3 also by 300mg, 400mg QD across all parts, For Part 3, include Pembrolizumab	SAC
4.2	PK	GSK- provided	Summary of Pembrolizumab Immunogenicity Data by Treatment and Study Day	Part 3 only	SAC
4.3	РК	PK06	Summary of Derived GSK3326595 Pharmacokinetic Parameters by Treatment and Study Day	PK parameters: Cmax, Tmax, Ctrough, AUC0-t, tlast, AUC0-tau, AUCinf, t½, λz , TI and AR determined from the concentration-time data in ng/ml; descriptive summaries: mean, SD, median, min, max, geometric mean & SD, CV%, and 95%CI of log-transformed	SAC

No.	Population	IDSL / Example Shell	Title	Programming Notes	Deliverable
				parameters, if applicable. by dose for Part 1, by cohort for parts 2 and 3 also by 300mg, 400mg QD across all parts	
4.5	PK	custom	Dose Proportionality Comparison (Power Model) for AUC(0-inf:=) and Cmax of GSK3326595	Provide separately for QD regimens and BID regimens of Part 1 only	SAC
4.6	PK	NA	Food Effect Sub-Study	<previously done=""></previously>	IA
4.7	PK	NA	Relative Bio-Availability Sub-Study	<previously done=""></previously>	IA

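### The SAP omits the protocol's power-model analysis of repeat-dose AUC(0-tau), names no study day for Cmax, and adds an undeclared three-values-per-dose rule

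*SAP*

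**What the plan says.** **Protocol 11.10.2.2.2.** If more than two dose cohorts are needed, proportionality is assessed for AUC and Cmax after a single dose. The same sentence extends the assessment to AUC(0-tau), "and Cmax following repeat dose administration will be assessed graphically and using the power model as described below". The slope is reported with a 90% confidence interval. No minimum number of values per dose is set.

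**SAP 9.2.2.1.** QD and BID are analysed separately. The parameters are AUC(0-inf) "or if not available AUC(0-t)) and Cmax will be assessed using the power model for, as described below". No study day is given and AUC(0-tau) is not mentioned. The section also states "A minimum of 3 values per dose must be available for a given parameter" and fits the power model only to levels that meet this.

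**SAP displays.** Table 4.5 is titled "Dose Proportionality Comparison (Power Model) for AUC(0-inf:=) and Cmax of GSK3326595". Figure 4.4 (dose proportionality figures) names neither parameter nor day. AUC(0-tau) is defined in SAP 9.2.1 and summarised by treatment and study day in Table 4.3.

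**SAP 2.1.** "There were no changes or deviations to the originally planned statistical analysis specified in the protocol amendment 8". The exceptions listed there do not mention dose proportionality or the three-value rule. Protocol 11.9.4 requires deviations from, and additions to, the protocol's analysis plan to be documented in the RAP.

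**Protocol 4.2.2.** During accelerated titration, "One subject at each dose level will be enrolled, starting at the dose described in Section 4.7". The same section lets further subjects be added at cleared levels for safety and PK reasons, and 4.2.3 moves to blocks of three once the toxicity trigger is met.

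**The concern.** A planned analysis disappears between protocol and SAP, and the SAP says that nothing changed. Someone programming from SAP 9.2.2.1 and the display list would produce no power-model slope for AUC(0-tau). They would also have to guess whether Cmax means Day 1, Day 15 or both.

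The drug is taken daily without planned breaks. Protocol 4.3.2 records a starting dose moved from 400 to 300 mg, with reduction to 200 mg for toxicity. How steady-state exposure scales with dose is therefore the more informative of the two questions, and Part 1 takes a serial Day 15 profile that can answer it (protocol Table 9).

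The three-value rule matters because a log-log regression draws much of its slope information from the extreme doses. A rule that removes thinly populated levels bears first on the lowest doses, which are where the design starts with one subject each.

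**Working it through.** **1. Side-by-side comparison**

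| Parameter | Protocol 11.10.2.2.2 | SAP 9.2.2.1 and Table 4.5 |
|---|---|---|
| Single-dose AUC | power model | AUC(0-inf), else AUC(0-t) |
| Single-dose Cmax | power model | Cmax, day not stated |
| Repeat-dose AUC(0-tau) | power model | absent |
| Repeat-dose Cmax | power model | Cmax, day not stated |
| Minimum values per dose | none | 3 |
| Change declared in SAP 2.1 | – | no |

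The protocol's condition of more than two dose cohorts is met for both regimens. SAP 5.1.1 lists eight QD levels (12.5, 25, 50, 100, 200, 300, 400, 600 mg) and four BID levels (50, 100, 150, 200 mg).

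**2. What the three-value rule could cost**

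Neither document gives a precision target for the slope or the number of PK values per level, so there is no stated figure to reproduce. What follows is an illustration under assumed counts, for QD single-dose data with one independent value per subject.

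With x = ln(dose), Var(slope) = σ²/Sxx, where Sxx = Σ n(x − x̄)². For a common σ, the ratio of the slope standard error with the rule to that without it is √(Sxx, all levels / Sxx, levels with n ≥ 3).

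Assume 3, 6, 3, 9 and 6 subjects at 100, 200, 300, 400 and 600 mg. A level with one value is dropped, and so is every other level with fewer than three.

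| Assumed n at 12.5, 25, 50 mg | Sxx, all | Sxx, kept | SE ratio | Increase in SE | Range kept |
|---|---|---|---|---|---|
| 1, 1, 1 | 26.34 | 8.20 | √(26.34/8.20) = 1.79 | 79% | 600/100 = 6-fold |
| 1, 1, 3 | 31.00 | 17.23 | √(31.00/17.23) = 1.34 | 34% | 600/50 = 12-fold |
| 1, 3, 3 | 39.88 | 32.16 | √(39.88/32.16) = 1.11 | 11% | 600/25 = 24-fold |
| 3, 3, 3 | 54.04 | 54.04 | 1.00 | 0% | 600/12.5 = 48-fold |

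The assumed counts at the higher levels also matter. With one value at each of 12.5, 25 and 50 mg and three at every other level, the ratio is √(20.76/5.64) = 1.92. With one value at 12.5 mg only and ten at every other level, it is √(86.41/80.28) = 1.04. If every level reaches three values, nothing is dropped.

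**3. The price of keeping single subjects**

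Leverage is 1/N + (x − x̄)²/Sxx. In the first row of the table N = 30, x̄ = 5.489 and ln(12.5) = 2.526. The 12.5 mg subject has leverage 1/30 + (2.526 − 5.489)²/26.34 = 0.37, against an average of 2/30 = 0.07.

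**The case against.** The strongest defence is that steady-state exposure by dose is still reported. Table 4.3 summarises AUC(0-tau), Cmax, the time-invariance ratio and the accumulation ratio by treatment and study day, by dose in Part 1. Figures 4.2 and 4.3 plot Day 1 and Day 15 profiles by dose level. Time invariance compares Day 15 AUC(0-tau) with Day 1 AUC(0-inf), so a reader could carry the single-dose finding over to steady state informally. Part 1 analyses are described as descriptive and exploratory, and no acceptance bound is attached to the slope. All of this stands and limits the seriousness. It does not supply the planned slope and interval, nor explain why SAP 2.1 is silent.

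On the three-value rule, the defence is that thin levels may not exist in the final data. Protocol 4.2.2 and 4.2.4.8 allow extra subjects at earlier levels, SAP 5.1.1 pools the PK/PD expansion subjects with their dose level, and alternative schedules such as BID escalate under 4.2.3 in blocks of three. This also stands: the loss cannot be read from the documents, and it mainly concerns QD.

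Three stronger readings are tempting but not supported:
- A reader might infer that repeat-dose Cmax has been dropped. The SAP names Cmax without a day, so it is unspecified.
- A reader might infer that one-subject levels are in fact discarded and that they anchor the slope. No counts per level are given.
- A reader might infer that the rule also excludes dose level 1, the reference for the fallback dose-normalised ratios. The rule is stated only for the power model; the fallback has its own condition of sufficient data.

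**Conclusion.** The main point holds on the text alone. The planned power-model analysis of repeat-dose AUC(0-tau) is missing from SAP 9.2.2.1 and Table 4.5, the study day for Cmax is unspecified, and neither is declared in SAP 2.1. For each regimen the AUC(0-tau) slope and its 90% interval are lost; the descriptive summaries remain. The analysis serves a secondary PK objective, so this should be corrected but does not threaten a primary endpoint.

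The secondary point holds in part. The three-value rule is new, undeclared and sits badly with one-subject titration. Its effect on the slope standard error runs from none to nearly double (ratios 1.00 to 1.92). These figures rest on assumed numbers per level, one independent value per subject and a common residual variance.

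**What to change.** 1. In SAP 9.2.2.1, Table 4.5 and Figure 4.4, add power-model fits and plots of Day 15 AUC(0-tau) and Day 15 Cmax, labelled separately from Day 1 AUC(0-inf) and Day 1 Cmax, for QD and for BID. If the sponsor does not want the repeat-dose analysis, its removal should be listed and justified in SAP 2.1.
2. Fit the power model to all subjects with an evaluable parameter, and report the number of values per dose beside each slope. Give the fit restricted to levels with at least three values as a sensitivity analysis, and list the rule in SAP 2.1 as an addition to the protocol.

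The cost is SAP wording and a few more model runs on parameters already derived. The downside is that single low-dose subjects carry high leverage in the unrestricted fit. Showing the restricted fit next to it lets the reader see whether the slope depends on them.

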9.2.2.2. Food Effect and Relative Bioavailability Sub-Study

Estimates of LS mean, LS mean difference and 95% CI are based on log transformed AUC(0-INF) and Cmax using a mixed-effect model with fixed-effect terms of fed status (fed or fasted), sequence and period and subject within sequence as a random effect. The

point estimates and their associated 90% CIs were then backtransformed to provide point estimates of the geometric LS mean, and 90% CIs and ratios of fed (test) vs. fasted (reference).

Programming note: Only use period 1 and period 2 data

```
ods output LSMeans=lsmean;
ods output estimates=estg;
ods output CovParms=Covsparms;
```

```
proc mixed data=pkparm1;

class sequence period treat subjid;

model Lcmax=sequence period treat/DDFM=SATTERTH;

random subjid(sequence);

lsmeans treat/pdiff cl alpha=0.1;

estimate 'Tablet Fed vs Tablet Fasted' treat 1 -1 / cl alpha=0.1;

run;
```

Where TREAT: FET = Tablet Fed; FFT = Tablet Fasted.

```
* Anti-log transformation to obtain the Geometric Means;
data glsmean;
set lsmean;
gmean=exp(estimate); *Geometric means;
run;
```

```
* Anti-log transformation to obtain the ratio of Geometric Means (point estimate) and its
90% confidence interval (lower and upper bounds);
data diffs;
set EST;
gratio=exp(estimate); ** Ratio of geometric mean;
glower=exp(lower); ** 90% CI lower bound;
gupper=exp(upper); ** 90% CI upper bound;
```

```
run;
```

```
**Calculate inter-subject CV and intra-subject CV;
DATA CV;
set Covsparms;
if covparm="subjid(sequence)" then intermse=estimate;
else if covparm="Residual" then intramse=estimate;
intercv = sqrt(exp(intermse) -1) *100;
intracv = sqrt(exp(intramse) -1) *100;
run;
```

Non-parametric methods such as the Hodges and Lehmann estimator (Hodges, 1963) will be used to estimate the median differences between the fed treatments and the fasted state treatments for tmax and $t\frac{1}{2}$. An associated 90% CI for the median differences will be constructed. The analysis will exclude data for a given period if the subject did not receive the correct dose or formulation during that period or the protocol-defined diet was not adhered to.

Based on the US FDA guidance on food-effect bioavailability studies, the absence of a food-effect will be established if the 90% CI of the ratio for Cmax and AUC, based on log-transformed data, is within the 80 to 125% equivalence limit. Recommendation on the clinical significance of the effect of food will be based on the magnitude of the change and our understanding of the exposure-clinical response relationship.

For the evaluation of food effect, tmax at fed and fasted status will be presented by subject and dose cohort in tabular and graphical form.

Relative Bioavailability of Tablet

Pharmacokinetic (PK) parameters $AUC_{0-\infty}$ (or if not available AUC(0-t)) and Cmax will be log-transformed and analyzed using a mixed-effects model with formulation (tablet or capsule)sequence and period as fixed effects, and subject as a random effect. Point estimates and their associated 90% CIs will be constructed for the differences between between tablet and capsule. The point estimates and their associated 90% CIs will then be back transformed to provide point estimates and 90% CIs for the ratios of tablet (test) vs. capsule (reference) under fasted condition.

Code will be consistent with the above for food effect analysis. The analysis will exclude data for a given period if the subject did not receive the correct dose or formulation during that period.

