Fasted: Subjects should take nothing by mouth apart from water and other medications for at least 8 hours before drug administration and should continue fasting until at least 4

hours after administration of the morning dose. Subjects should be administered the drug product as a capsule or tablet (as indicated) with 200 mL (8 fluid ounces) of water. Water can be allowed, as desired, except for one hour before and after drug administration. All subjects will receive standardized meals at approximately 4- and 9- hours post dose. Additional details of the meals will be provided in the SRM.

Fed: Following an overnight fast (at least 8 hours), subjects should start the recommended high fat, high calorie breakfast 30 minutes prior to administration of the GSK3326595. Study subjects should eat this meal in 30 minutes or less; however, GSK3326595 should be administered 30 minutes after start of the meal. The GSK3326595 should be administered as a tablet with 200 mL (8 fluid ounces) of water. No food should be allowed for at least 2 hours post-dose. Water can be allowed, as desired, except for one hour before and after drug administration. All subjects will receive standardized meals at approximately 4- and 9- hours post dose. Further details of the meals will be provided in the SRM.

Any subject who experiences vomiting within 3 hours of dosing will be removed from the statistical analysis of PK comparability between tablet/capsule and tablet (fasted)/tablet (fed), and additional subjects will be enrolled to ensure 12 subjects complete all three periods.

As described in Section 8.2.2, the Day 4 (Period 2) visit may be performed on Day 4 or Day 5. The Day 8 (Period 3) visit (capsule administered in a fasting state) may be performed ± 1 day. Continuous daily dosing with GSK3326595 will only commence once the subject has completed the Period 3 visit, irrespective of whether that visit occurs ± 1 day.

If the GSK3326595 tablet bioavailability is comparable to that of the GSK3326595 capsules, all new and ongoing subjects may be switched from capsules to tablets for the remainder of the study, once they have been notified by the Sponsor.

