11.10.2.2.3. Food Effect and Relative Bioavailability Sub-Study

Pharmacokinetic (PK) parameters AUC($0-\infty$), and Cmax will be log-transformed and analyzed separately using a mixed-effects model with fixed-effect term for fed status (fed or fasted)/formulation (tablet or capsule), and subject as a random effect. Point estimates and their associated 90% CIs will be constructed for the differences between fed and in fasted state, between tablet and capsule. For the relative bioavailability analysis, tablets are the test formulation and capsules are the reference. The point estimates and their associated 90% CIs were then back transformed to provide point estimates and 90% CIs for the ratios of fed/fasted and tablet/capsule. Non-parametric methods such as the Hodges and Lehmann estimator will be used to estimate the median differences between

the fed treatments and the fasted state treatments for tmax and $t^{1/2}$. An associated 90% CI for the median differences will be constructed.

Based on the US FDA guidance on food-effect bioavailability studies, the absence of a food-effect will be established if the 90% CI of the ratio for Cmax and AUC, based on log-transformed data, is within the 80 to 125% equivalence limit. Recommendation on the clinical significance of the effect of food will be based on the magnitude of the change and our understanding of the exposure-clinical response relationship.

For the evaluation of food effect, tmax at fed and fasted status will be presented by subject and dose cohort in tabular and graphical form.

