Subjects enrolled in the sub-study will be assigned to one of two sequences, as described in Table 1; equal numbers will be assigned to each sequence.

Table 1 Food Effect and Relative Bioavailability Sub-Study

Sample Size	Sequence	Period 1 (D1)	Period 2 (D4)	Period 3 (D8)
6	1	Fasted / tablet	Fed / tablet	Fasted / capsule
6	2	Fed / tablet	Fasted / tablet	Fasted / capsule

Fasted: Subjects should take nothing by mouth apart from water and other medications for at least 8 hours before drug administration and should continue fasting until at least 4 hours after administration of the morning dose. Subjects should be administered the drug product as a capsule or tablet (as indicated) with 200 mL (8 fluid ounces) of water. Water

can be allowed, as desired, except for one hour before and after drug administration. All subjects will receive standardized meals at approximately 4- and 9- hours post dose. Additional details of the meals will be provided in the SRM.

Fed: Following an overnight fast (at least 8 hours), subjects should start the recommended high fat, high calorie breakfast 30 minutes prior to administration of the GSK3326595. Study subjects should eat this meal in 30 minutes or less; however, GSK3326595 should be administered 30 minutes after start of the meal. The GSK3326595 should be administered as a tablet with 200 mL (8 fluid ounces) of water. No food should be allowed for at least 2 hours post-dose. Water can be allowed, as desired, except for one hour before and after drug administration. All subjects will receive standardized meals at approximately 4- and 9- hours post dose. Further details of the meals will be provided in the SRM.

Any subject who experiences vomiting within 3 hours of dosing will be removed from the statistical analysis of PK comparability between tablet/capsule and tablet (fasted)/tablet (fed), and additional subjects will be enrolled to ensure 12 subjects complete all three periods.

The Day 4 (Period 2) visit may be performed on Day 4 or Day 5. The Day 8 (Period 3) visit (capsule administered in a fasting state) may be performed ± 1 day. Continuous daily dosing with GSK3326595 will only commence once the subject has completed the Period 3 visit, irrespective of whether that visit occurs ± 1 day.

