3.3. Final Analyses

The final analysis of the study will be performed after the completion of the following sequential steps: As per Protocol Amendment 8 implementation, final analysis will be performed following the data cut off (DCO). This will occur when all subjects have either died, discontinued treatment (including 30-day safety follow up), withdrawn consent, or have consented to continue with treatment as defined in Protocol Amendment 8.

All required database cleaning activities have been completed and final database release (DBR), source data lock (SDL) and database freeze (DBF) have been declared by Data Management.

Data from the three parts may be combined for some analyses at the end of the trial, as appropriate. All primary and secondary analyses will be conducted for the final analysis.

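### The SAP's tablet-versus-capsule model includes period, but the capsule is given only in Period 3, so the planned ratio and 90% CI cannot be estimated, and the departure from the protocol model is not declared.

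*SAP*

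**What the plan says.** The sub-study design is the same in both documents (Protocol 4.2.6, Table 2; SAP 2.3.1, Table 1). Sequence 1 is tablet fasted, tablet fed, capsule fasted. Sequence 2 is tablet fed, tablet fasted, capsule fasted. The protocol text confirms where the capsule falls: "The Day 8 (Period 3) visit (capsule administered in a fasting state) may be performed" within one day of its nominal date.

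Protocol 11.10.2.2.3 analyses log AUC and log Cmax with a "mixed-effects model with fixed-effect term for fed status (fed or fasted)/formulation (tablet or capsule), and subject as a random effect". It has no period or sequence term.

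SAP 9.2.2.2, under Relative Bioavailability of Tablet, replaces this with "formulation (tablet or capsule)sequence and period as fixed effects, and subject as a random effect" and calls for a back-transformed tablet/capsule ratio and 90% CI in the fasted state. It adds: "Code will be consistent with the above for food effect analysis". In that food-effect code, period is listed in the CLASS statement, and the code is preceded by "Programming note: Only use period 1 and period 2 data".

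SAP 2.1 states: "There were no changes or deviations to the originally planned statistical analysis specified in the protocol amendment 8". It then lists exceptions, none of which mentions this model. SAP 3.3 states: "All primary and secondary analyses will be conducted for the final analysis". In SAP 15.12.9 the relative-bioavailability table (4.7) is noted as done earlier, with the interim analysis as its deliverable.

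**The concern.** A period effect can be separated from a formulation effect only if each formulation appears in more than one period, or if some period contains both formulations. Neither is true here, so a model containing both terms cannot return the quantity the SAP promises.

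Relative bioavailability is a stated secondary objective of Part 1. If the SAP stands, the described analysis cannot be reproduced, and the text misdescribes the model behind any ratio already reported. A reader who sees period in the model would also conclude that the ratio has been adjusted for period, when it is fully confounded with Period 3.

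**Working it through.** The documents give no numerical result, power or CV for this comparison, so there is no figure to reproduce. The check is one of estimability.

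**Design (both documents)**

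| | Period 1 | Period 2 | Period 3 |
|---|---|---|---|
| Sequence 1 | tablet fasted | tablet fed | capsule fasted |
| Sequence 2 | tablet fed | tablet fasted | capsule fasted |

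**Algebra for the fasted records.** Write the mean log parameter as μ + s(i) + p(j) + f(k), for sequence i, period j and formulation k. The within-subject tablet minus capsule difference has expectation

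- Sequence 1: p(1) − p(3) + f(T) − f(C)
- Sequence 2: p(2) − p(3) + f(T) − f(C)

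The terms p(3) and f(C) appear only as the sum p(3) + f(C). Adding any constant to f(C) and subtracting it from p(3) leaves every cell mean unchanged, so f(T) − f(C) can take any value.

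**Rank check.** A contrast L is estimable only if adding it as a row to the design matrix X leaves the rank unchanged.

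| Records | Fixed effects | Contrast | Rank of X | Rank of X with L | Estimable |
|---|---|---|---|---|---|
| Fasted | sequence, period, formulation (SAP) | tablet − capsule | 4 | 5 | no |
| All | sequence, period, two-level formulation | tablet − capsule | 4 | 5 | no |
| All | sequence, period, three-level treatment | fasted tablet − capsule | 5 | 6 | no |
| All | sequence, period, three-level treatment | fed − fasted tablet | 5 | 5 | yes |
| Fasted | formulation only | tablet − capsule | 2 | 2 | yes |
| All | one three-level term, no period or sequence (protocol) | fasted tablet − capsule | 3 | 3 | yes |

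The ranks of the models with period are the same with 12 subjects per sequence as with 6. A random subject effect does not help, because the aliasing is in the fixed effects. The food-effect contrast is sound, so the defect is specific to formulation.

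**Period restriction.** If the food-effect code's restriction to Periods 1 and 2 were carried over, 0 of the 4 remaining sequence-period cells would contain a capsule record.

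**After period is dropped.** Let e be the multiplicative Period 3 effect relative to Periods 1 and 2. The estimated ratio is then the true ratio divided by e. No value of e is given in the documents; the following are assumptions, with a true ratio of 1:

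- e = 0.9: 1/0.9 = 1.11
- e = 1.1: 1/1.1 = 0.91
- e = 1.2: 1/1.2 = 0.83

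A simulation with 12 subjects (2,000 runs) gave 1.112 for e = 0.9 and 0.909 for e = 1.1. With an assumed within-subject CV of 30% and 12 subjects, the nominal 90% CI covered the true ratio in 90%, 79% and 46% of simulated trials for e = 1.0, 0.9 and 0.8.

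**Can the data test for a Period 3 effect?** On the tablet records, Period 1 versus Period 2 is estimable (rank 4 and 4). Period 3 versus the mean of Periods 1 and 2 is not: the rank goes from 4 to 5 on tablet data and from 5 to 6 on all data.

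**The case against.** The aliasing itself is not open to dispute. The objections concern what follows from it.

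- **The analysis may not be rerun.** SAP 9.2.2 makes the PK statistical analyses conditional on sufficient data, and Table 4.7 is listed as an interim deliverable already produced. This stands as a description of the schedule, but it sharpens the reporting problem: a ratio in that table cannot have come from the model written in the SAP.
- **A programmer would adapt the code.** The Period 1 and 2 restriction sits under the food-effect model, and a fasted tablet-capsule comparison plainly needs Period 3. That is fair, so the restriction is a matter of clarity only. The period term is different: it is in the SAP's prose, and omitting it departs from the plan. Period as a linear covariate would be estimable, but the SAP code makes it categorical.
- **Sequence need not go.** Sequence plus formulation is estimable on the fasted records (rank 3). This stands; removing sequence is a choice, made because it returns to the protocol model.
- **Carry-over is probably small and can be examined.** Protocol 7.1.3 gives a plasma half-life of 3 to 6 hours (species not stated), and doses are at least 48 hours apart. At 6 hours that is 48/6 = 8 half-lives, leaving 1/256, about 0.4%. Pre-dose samples are also scheduled on Days 1, 4 and 8 (Protocol Table 13). This stands for residual drug. It does not address other Period 3 effects.
- **Little depends on the result.** No numeric criterion governs the switch to tablets, the 80 to 125% limits are stated for food effect only, and the decision to combine tablet and capsule cohorts was communicated on 3 November 2021, before SAP version 1.0 of 8 September 2022. This stands and limits the consequence.

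**Conclusion.** The concern holds. As written, SAP 9.2.2.2 cannot produce a tablet/capsule ratio or its 90% CI, at any sample size. This follows from the two sequences and the categorical period term, and needs no outside assumption. The protocol's model is estimable, so the failure comes from the period term that the SAP added without declaring it in 2.1. Protocol 11.9.4 requires such additions to be documented in the analysis plan.

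The effect is on reporting and interpretation. Nothing in the documents shows that a decision depended on the written model. Once period is removed, the ratio is estimable only on the assumption of no Period 3 effect, which this design cannot test. The 1.11, 0.91 and 0.83 figures show how such an effect would pass through; they are not evidence that one exists. This should be fixed, and confidence in the finding is high.

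**What to change.** 1. In SAP 9.2.2.2, remove period from the relative-bioavailability model. Fit log AUC and log Cmax with formulation fixed and subject random, on the fasted tablet and fasted capsule records. Describe this as the protocol's formulation-plus-random-subject model restricted to fasted records, and state that the Period 1 and 2 restriction does not apply.
2. In SAP 2.1, record the restriction to fasted records. Record there too the sequence and period terms added to the food-effect model, which the protocol model also lacks; they are estimable but undeclared.
3. Confirm and document which model produced the existing Table 4.7, and rerun it if it differs.
4. Report with the ratio that it is fully confounded with any Period 3 or carry-over effect and assumes none. The Day 8 pre-dose concentrations can inform the carry-over part. A Period 1 versus Period 2 tablet comparison may be shown only as indirect information, because it cannot test for a Period 3 effect.

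The cost is wording in two SAP sections, one program check and possibly a rerun on about 12 subjects, with no new data. The drawback is that the result carries an openly stated assumption that cannot be tested.
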